Clinically significant abnormal laboratory or other examination (e.g. electrocardiogram) findings independent from the underlying medical condition that are detected during the study or are present at prior to Day 0 and significantly worsen during the study should be reported as adverse events. The Investigator will exercise his or her medical and scientific judgment in deciding whether an abnormal laboratory finding, or other abnormal assessment is clinically significant. Clinically significant abnormal laboratory values occurring during the clinical study will be followed until repeat tests return to normal, stabilize, or are no longer clinically significant. Any abnormal test that is determined to be an error does not require reporting as an adverse event.

Worsening of the index infection due to insufficient therapeutic effect of study drug is captured as an efficacy measure (i.e., clinical failure) and in general will not be considered an AE. However, if the worsening of the index infection meets seriousness criteria (see Section 8.3), the event will be deemed an SAE.

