8.3.3 Assessment of Adverse Events by the Investigator

Unless an adverse event is considered serious and meets SAE criteria, progression or worsening of the index infection due to insufficient effect of study drug should not be deemed an AE or deemed related to study drug.

The Investigator will assess the severity (intensity) of each adverse event as mild, moderate, or severe, and will also categorize each adverse event as to its potential relationship to study drug using the categories of “yes” or “no”.

Assessment of Severity:

Mild – An event that is easily tolerated and generally not interfering with normal daily activities.

Moderate – An event that is sufficiently discomforting to interfere with normal daily activities.

Severe – An event that is incapacitating with inability to work or perform normal daily activities.

Causality Assessment:

The relationship of an adverse event to the administration of the study drug is to be assessed according to the following definitions:

No (unrelated, not related, no relation) – The time course between the administration of study drug and the occurrence or worsening of the adverse event rules out a causal relationship and another cause (concomitant drugs, therapies, complications, etc.) is suspected.

Yes (related) – The time course between the administration of study drug and the occurrence or worsening of the adverse event is consistent with a causal relationship and no other cause (concomitant drugs, therapies, complications, etc.) can be identified.

The definition implies a reasonable possibility of a causal relationship between the event and the study drug. This means that there are facts (evidence) or arguments to suggest a causal relationship.

The following factors should also be considered:

- The temporal sequence from study drug administration: The event should occur during or after the study drug is administered. The length of time from study drug exposure to event should be evaluated in the clinical context of the event.
- Underlying, concomitant, intercurrent diseases: Each report should be evaluated in the context of the natural history and course of the disease being treated and any other disease the subject may have.
- Concomitant drug: The other drugs the subject is taking or the treatment the subject receives should be examined to determine whether any of them might be recognized to cause the event in question.

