8.4 Serious Adverse Events

An adverse event or adverse reaction is considered serious if, in the view of either the Investigator or Sponsor, it results in any of the following outcomes:

- Death,
- A life-threatening adverse event,
 - NOTE: An adverse event or adverse reaction is considered “life-threatening” if, in view of either the Investigator or Sponsor, its occurrence places the subject at immediate risk of death. It does not include an event that, had it occurred in a more severe form, might have caused death.
- Requires hospitalization or prolongation of existing hospitalizations,
 - NOTE: Any hospital admission with at least one overnight stay will be considered an inpatient hospitalization. An emergency room visit without hospital admission will not be recorded as a serious adverse event (SAE) under this criterion, nor will hospitalization for a procedure scheduled or planned before signing of informed consent. However, unexpected

complications and/or prolongation of hospitalization that occur during elective surgery should be recorded as adverse events and assessed for seriousness. Admission to the hospital for social or situational reasons (i.e., no place to stay, live too far away to come for hospital visits) will not be considered inpatient hospitalizations.

- A persistent or significant disability/incapacity or substantial disruption of the ability to conduct normal life functions,
- A congenital anomaly or birth defect,
- An important medical event.
 - NOTE: Important medical events that may not result in death, be life-threatening, or require hospitalization may be considered an SAE when, based upon appropriate medical judgment, they may jeopardize the subject and may require medical or surgical intervention to prevent one of the outcomes listed above. Examples of such medical events include allergic bronchospasm requiring intensive treatment in an emergency room or at home, blood dyscrasia or convulsions that do not result in inpatient hospitalizations, or the development of drug dependency.

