
#### 4. SAMPLE SIZE DETERMINATION

The primary efficacy endpoint is the proportion of subjects with Clinical Cure at Day 21.

It is assumed that the proportion of subjects with Clinical Cure will be 65% in the placebo group, and 85% in the 20 mg/kg dose group. With 69 subjects per group, there will be >90% power for a statistically significant difference at a two-sided 0.05 level of significance. Sample size calculation was performed based on Fisher's Exact test using binomial enumerations (PASS version 14). Assuming a 10% drop-out rate, approximately 154 subjects (77 per group) will be randomized.

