### **6.6.1. Adverse Events**

An AE is defined as any untoward medical occurrence in a clinical investigation subject administered a pharmaceutical product, which does not necessarily have a causal relationship with this treatment. Adverse events, which include clinical laboratory test variables, will be monitored and documented from the time of randomization until 28 days after last dose. Adverse events will be coded using MedDRA (Version 19.1). Treatment-emergent adverse events (TEAEs) are defined as AEs that start on or after the administration of the study drug.

An overview of AEs will be provided including counts and percentages of subjects with the following:

- Any AEs
- Any TEAEs (overall and by maximum severity)
- Any drug-related TEAEs (overall and by maximum severity)
- Any serious AEs (SAEs) (overall and by maximum severity)
- Any drug-related serious AEs (overall and by maximum severity)
- Any treatment-emergent serious AEs (TESAEs)
- Any TEAEs leading to discontinuation of study drug
- Any AEs leading to death

The number and percentage of subjects with at least one TEAE will be presented by system organ class and preferred term. Drug-related TEAE, SAEs, Drug-related SAEs, and TESAEs will be summarized in the same manner. In the case of multiple occurrences of the same AE within the same subject, each subject will be counted only once for each SOC and preferred term.

Summaries will be provided by maximum severity for the number and percentage of subjects with TEAEs by system organ class and preferred term. For this summary, subjects with multiple adverse events will be counted only once by the maximum severity with in an SOC and preferred term.

Subject listings of SAEs, TEAEs leading to discontinuation of study drug, and AEs leading to death will be provided. All adverse events will be listed.

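### The pooled SAE, TESAE and fatal-AE rows include serious worsening of the index pneumonia, and no planned table counts subjects without it

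*Protocol*

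**What the plan says.** Protocol section 8.3 (Adverse Events) states that worsening of the index infection through insufficient drug effect is "captured as an efficacy measure (i.e., clinical failure) and in general will not be considered an AE". It then adds an exception: "if the worsening of the index infection meets seriousness criteria (see Section 8.3), the event will be deemed an SAE". Section 8.3.3 repeats the rule for investigators: unless the event is serious, "progression or worsening of the index infection due to insufficient effect of study drug should not be deemed an AE".

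The seriousness criteria are in section 8.4, not in 8.3 as the cross-reference says. They include death, life-threatening events and "Requires hospitalization or prolongation of existing hospitalizations".

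The overview in SAP section 6.6.1 counts subjects with any SAE, with any TESAE ("Any treatment-emergent serious AEs (TESAEs") and with any AE leading to death. No row flags or excludes worsening of the index pneumonia. The same section plans finer output: "The number and percentage of subjects with at least one TEAE will be presented by system organ class and preferred term", with the same layout for SAEs, drug-related SAEs and TESAEs, and subject listings of SAEs and fatal AEs. SAP section 6.4.2.2 tabulates pneumonia-related mortality by arm in the micro-ITT population. SAP section 6.6 summarizes safety by treatment received in the Safety Population and specifies no test.

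**The concern.** The plan assigns worsening pneumonia to efficacy, then returns the serious cases to the safety totals. The subjects are ventilated ICU patients, so a worsening pneumonia can readily meet a seriousness criterion. If the drug raises the cure rate as hoped, the active arm should have fewer such events. Its SAE total then falls for an efficacy reason, and that fall can offset a real excess of other serious events. If there is no such excess, the same fall looks like a safety advantage.

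Clinical safety and tolerability is a primary objective (protocol section 2.2, SAP section 2.2). A reader who compares the arms on the overview rows cannot tell which explanation applies.

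**Working it through.** **Inputs from the documents**

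- Cure rates: "It is assumed that the proportion of subjects with Clinical Cure will be 65% in the placebo group", and 85% on active (SAP section 4). Non-cure is therefore 35% and 15%.
- Arm size: 69 / 0.90 = 76.7, rounded up to 77 per arm. This matches the plan's allowance for 10% drop-out.
- The documents give no SAE rate, so there is no planned SAE figure to reproduce.

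**Assumptions**

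- *s*, the share of non-cures recorded as serious worsening: varied from 10% to 80%.
- *o*, the rate of other SAEs: 20% on placebo and 30% on active.
- The two kinds of event are independent.
- Non-cure (*f*) is taken as an upper bound for worsening.

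**Formula**

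Any-SAE rate = 1 − (1 − *f*·*s*)(1 − *o*).

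Example with *s* = 60%:

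- Placebo: *f*·*s* = 0.35 × 0.60 = 0.21, so 1 − 0.79 × 0.80 = 36.8%.
- Active: *f*·*s* = 0.15 × 0.60 = 0.09, so 1 − 0.91 × 0.70 = 36.3%.

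The assumed 10-point excess of other SAEs has disappeared from the total. The last column below is the probability, enumerated exactly from two binomials with n = 77, that the observed active rate is at or below the placebo rate.

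| Serious share *s* | Placebo any-SAE | Active any-SAE | Active looks no worse |
|---|---|---|---|
| Index events excluded | 20.0% | 30.0% | 9% |
| 10% | 22.8% | 31.1% | 14% |
| 20% | 25.6% | 32.1% | 21% |
| 40% | 31.2% | 34.2% | 38% |
| 60% | 36.8% | 36.3% | 56% |
| 80% | 42.4% | 38.4% | 72% |

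**Dependence on efficacy, at *s* = 60%**

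- No efficacy (non-cure 35% in both arms): active = 1 − 0.79 × 0.70 = 44.7%. It looks no worse in 18% of trials.
- Half the assumed benefit (cure 75%, non-cure 25%): active = 1 − 0.85 × 0.70 = 40.5%. It looks no worse in 35%.

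**No true excess (*o* = 20% in both arms)**

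- *s* = 60%: active = 1 − 0.91 × 0.80 = 27.2% against 36.8% on placebo, an apparent advantage of 9.6 points.
- *s* = 10%: active = 1 − 0.985 × 0.80 = 21.2% against 22.8%, an apparent advantage of 1.6 points.

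**What the planned outputs separate**

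- Preferred-term tables put other kinds of event on their own rows. They do not give the number of subjects with at least one SAE other than index-pneumonia worsening.
- AEs leading to death get an overview count and a listing, with no preferred-term table of their own.
- Pneumonia-related mortality separates deaths only. It does so in micro-ITT by randomized arm, not in the Safety Population by treatment received.

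**The case against.** The strongest reply is that the plan already separates much of this. An excess of a different serious event has its own preferred-term row and cannot be cancelled there. Listings allow case review. Non-pneumonia deaths by arm follow by subtraction in micro-ITT. The drug-related SAE row should hold few index-pneumonia events, because protocol section 8.3.3 reserves a related judgment for events with no other identifiable cause. The DMC sees unblinded data. No SAE test, margin or success rule exists to be biased. All of this stands, and it confines the point to the pooled rows.

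It does not remove the point. The related-only row also drops genuine harms for which an ICU patient offers another explanation. DMC review protects the running trial but does not shape the final tables. Classifying SAEs is not in the adjudication committee's stated remit (protocol section 9.5).

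A reader might infer three stronger things that the documents do not support:

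- *That preferred-term tables cannot help because fatal pneumonia will be coded as septic shock or organ failure.* No section says so, and section 8.3 asks for a disease or syndrome in preference to its signs and symptoms. Some leakage is possible, as is confusion with re-infection or new pneumonia, but neither is documented.
- *That most failures become SAEs.* Non-cure is not worsening. A stable, unresolved pneumonia is a non-cure without worsening, and the protocol records persistence and re-infection as separate states. The serious share is unknown.
- *That the safety objective cannot be answered.* It also rests on individual AEs, laboratory results, vital signs and immunogenicity.

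**Conclusion.** The point holds in a limited form. The any-SAE, any-TESAE and fatal-AE totals mix efficacy with safety. No planned output gives a by-arm subject count of SAEs or fatal AEs without index-pneumonia worsening in the Safety Population.

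The direction of the effect follows from the plan's own hypothesis that the drug improves cure. The size does not follow from the documents, because they give neither the serious share nor the rate of other SAEs. In the illustration, the chance that a 10-point excess of other SAEs goes unseen in the total rises from 9% to between 14% and 72%. Near-complete masking needs both the full 20-point cure benefit and a high serious share. Without efficacy, events common to both arms only dilute the comparison (18% at a 60% share). Independence is also doubtful, since a serious non-pneumonia event can itself prevent cure.

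This is a worthwhile, low-cost improvement to the reporting. It is not a flaw that invalidates the safety analysis.

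**What to change.** 1. Add one yes/no item to the SAE form: worsening of the index pneumonia. Have it confirmed by blinded review before unblinding, because attribution made afterwards would carry little weight.
2. In SAP section 6.6.1, present SAEs, TESAEs and AEs leading to death by arm twice in the Safety Population: for all events, and excluding flagged events. Keep the all-events table as the main one, and leave SAE reporting duties unchanged.
3. Correct the cross-reference in protocol section 8.3 so that it points to section 8.4 for the seriousness criteria.

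The cost is one eCRF item, a blinded check, and a repeat of three summaries. The downside is some judgment in setting the flag. Blinding limits this, and the full table remains beside the restricted one.

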8.3.1 Adverse (Drug) Reaction

All noxious and unintended responses to a medicinal product related to any dose should be considered an adverse drug reaction. “Responses” to a medicinal product means that a causal relationship between a medicinal product and an adverse event is at least a reasonable possibility, i.e. the relationship cannot be ruled out.

8.3.2 Unexpected Adverse Drug Reaction

An Unexpected Adverse Drug Reaction is defined as an adverse reaction, the nature or severity of which is not consistent with the applicable product information. For Aerucin[®], the reference safety information is included in 7.1 of the Investigator’s Brochure currently in force. The reference safety information will be reviewed yearly, and the periodicity of the review will be harmonized with the reporting period of the Development Safety Update Report.

8.3.3 Assessment of Adverse Events by the Investigator

Unless an adverse event is considered serious and meets SAE criteria, progression or worsening of the index infection due to insufficient effect of study drug should not be deemed an AE or deemed related to study drug.

The Investigator will assess the severity (intensity) of each adverse event as mild, moderate, or severe, and will also categorize each adverse event as to its potential relationship to study drug using the categories of “yes” or “no”.

Assessment of Severity:

Mild – An event that is easily tolerated and generally not interfering with normal daily activities.

Moderate – An event that is sufficiently discomforting to interfere with normal daily activities.

Severe – An event that is incapacitating with inability to work or perform normal daily activities.

Causality Assessment:

The relationship of an adverse event to the administration of the study drug is to be assessed according to the following definitions:

No (unrelated, not related, no relation) – The time course between the administration of study drug and the occurrence or worsening of the adverse event rules out a causal relationship and another cause (concomitant drugs, therapies, complications, etc.) is suspected.

Yes (related) – The time course between the administration of study drug and the occurrence or worsening of the adverse event is consistent with a causal relationship and no other cause (concomitant drugs, therapies, complications, etc.) can be identified.

The definition implies a reasonable possibility of a causal relationship between the event and the study drug. This means that there are facts (evidence) or arguments to suggest a causal relationship.

The following factors should also be considered:

- The temporal sequence from study drug administration: The event should occur during or after the study drug is administered. The length of time from study drug exposure to event should be evaluated in the clinical context of the event.
- Underlying, concomitant, intercurrent diseases: Each report should be evaluated in the context of the natural history and course of the disease being treated and any other disease the subject may have.
- Concomitant drug: The other drugs the subject is taking or the treatment the subject receives should be examined to determine whether any of them might be recognized to cause the event in question.
- Known response pattern for this class of study drug: Clinical and/or preclinical data may indicate whether a particular response is likely to be a class effect.
- Exposure to physical and/or mental stresses: The exposure to stress might induce adverse changes in the recipient and provide a logical and better explanation for the event.
- The pharmacology and pharmacokinetics of the study drug: The known pharmacologic properties (absorption, distribution, metabolism, and excretion) of the study drug should be considered.

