Study subjects will receive a single treatment dose (at Day 0) in addition to SOC antibiotic treatment, and then enter a safety, efficacy and PK follow-up study period for a total study duration of 28 days. The selection of SOC antibiotics is made in accordance with local best practices at the discretion of the investigator and should not exceed the duration of 14 days.

The clinical course of pneumonia will be assessed daily by the investigator. Once Clinical Cure has been determined, the clinical status of the subject will be monitored to confirm continuation of Clinical Cure, re-infection (pneumonia due to *P. aeruginosa*), or new infection (pneumonia due to an unknown pathogen or a pathogen other than *P. aeruginosa*). "Clinical Cure" will be declared at any time during the study by the PI, provided that the required criteria are met either based on documented improvements in signs and symptoms, +/- changes documented by chest X-ray (if performed as part of SOC), as interpreted by the investigator.

The assessment of Clinical Cure (resolution of pneumonia) by the site investigator will be used for the primary analysis. An adjudication committee will apply newly defined Clinical Cure criteria post hoc in a secondary analysis. “Clinical Cure” will be assessed for analytical purposes on Day 7, 14, 21 (primary efficacy endpoint) and 28.

Clinical safety assessments will be performed on an ongoing basis while predefined laboratory assessments will be performed at baseline, and thereafter at Day 4, 7, 14, 21, and 28. Test results obtained for medical reasons between these mandatory time points will be assessed for adverse events and documented accordingly.

Secondary efficacy endpoints will be assessed in a similar manner during the 28-day period when appropriate, daily when possible, (e.g., Time on mechanical ventilation including if tracheostomy is in place; Time on supplemental oxygenation; measures of respiratory health such as changes in PaO₂/FiO₂ using arterial blood gases and/or pulse oximetry measurements), or upon occurrence (e.g., antibiotic utilization, duration of stay in the ICU, duration of hospitalization, duration of intubation with ventilation, or duration of mechanical ventilation if tracheostomy in place).

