 - a. An airway specimen culture positive by any method for *P. aeruginosa* of a specimen obtained less than 72 hours prior to randomization. A fresh airway specimen must be obtained prior to treatment initiation for standard microbial culture by the local laboratory (including organism identification, quantitative/semi-quantitative culture and susceptibility testing); the corresponding culture results are NOT required prior to randomization.

OR
 - b. A rapid diagnostic test (see section 14.3 for acceptable methods). In such case, the same sample must ALSO be used for standard microbial culture by the local laboratory (including organism identification, quantitative/semi-quantitative culture and susceptibility testing). The corresponding culture results are NOT required prior to randomization.

OR
 - c. A positive airway specimen culture by any method of *P. aeruginosa* from a specimen obtained at screening (quantitative, semi-quantitative).
8. APACHE II score ≥ 10 and ≤ 35 within 24 hours once subject has consented.

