9.4 Data Monitoring Committee (DMC)

An independent DMC will be reviewing on a regular basis the safety information collected to-date. The corresponding procedures will be defined in a charter. DMC meetings will include a blinded session, when personnel in charge of the study will provide background information to facilitate review, and an open session, closed to all but DMC members, during which access to unblinded reports and/or subject-specific data will be allowed.

In addition, all SAEs deemed related will be communicated to the DMC, as defined in the charter, for immediate review.

The Medical Monitor will call for a meeting of the DMC whenever safety concerns of immediate significance may arise, such as abnormal frequency of non-serious events or unrelated events.

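### The yes/no causality definitions in Protocol 8.3.3 are not complements and conflict with 8.3.1, so relatedness is likely to be flagged inconsistently

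*Protocol*

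**What the plan says.** Protocol Section 8.3.3 asks the investigator to "categorize each adverse event as to its potential relationship to study drug using the categories of “yes” or “no". No third category is offered.

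- *No* applies when the time course "rules out a causal relationship and another cause (concomitant drugs, therapies, complications, etc.) is suspected".
- *Yes* applies when the time course "is consistent with a causal relationship and no other cause (concomitant drugs, therapies, complications, etc.) can be identified".

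The next sentence comments on this: "The definition implies a reasonable possibility of a causal relationship between the event and the study drug". A list follows of factors to take into account, among them underlying disease and concomitant drugs.

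Section 8.3.1 sets the standard for an adverse reaction differently. A causal relationship is accepted when it "is at least a reasonable possibility, i.e. the relationship cannot be ruled out". Nothing there depends on the absence of another cause.

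The yes/no answer is then used elsewhere:

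- Protocol 9.4 says that "all SAEs deemed related will be communicated to the DMC", for immediate review under the charter.
- Protocol 8.5 asks for SAEs after the 28-day period only if the investigator considers them related.
- SAP 6.6.1 tabulates drug-related TEAEs and drug-related SAEs.

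**The concern.** A two-way classification works only if every event falls on one side and the dividing line is the same wherever it is applied. Here each definition joins two conditions, and neither definition is the negation of the other. An event can satisfy one half of each and so qualify for neither. For the most ordinary case in this population, plausible timing with some other possible explanation, Sections 8.3.1 and 8.3.3 do not give the same answer.

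What is at stake is the sensitivity and consistency of the related flag. Two investigators could mark the same event differently and each point to protocol text in support. An event marked *No* on the strict reading would miss immediate DMC communication and the drug-related tables. If it occurred after the 28-day period, it would not be reportable under 8.5 at all. The human exposure that the protocol cites is 16 healthy volunteers, 5 of them at the study dose (Table 1-1), so little is known in advance about which events to expect in critically ill patients.

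**Working it through.** There is no stated figure to reproduce. The check sets the definitions side by side.

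**Step 1. Classify every combination.** Take timing as either consistent with the drug or excluding it, and another possible cause as either absent or present.

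| Timing | Other cause | 8.3.3 | 8.3.1 |
|---|---|---|---|
| Consistent | Absent | Yes | Reaction |
| Consistent | Present | Neither | Reaction |
| Excludes drug | Absent | Neither | Not a reaction |
| Excludes drug | Present | No | Not a reaction |

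Two of the four cells have no category in 8.3.3. The second row is the important one: a reaction under 8.3.1 that cannot be *Yes* under 8.3.3. That row assumes that the other cause is possible rather than proven. If it were established firmly enough to exclude the drug, 8.3.1 would not call the event a reaction either. Treating timing as two-valued is also a simplification, since an unclear time course would meet neither definition.

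**Step 2. See where this trial's events are likely to fall.**

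- *Other causes.* Protocol 3.1 states: "Study subjects will receive a single treatment dose (at Day 0) in addition to SOC antibiotic treatment". Protocol 4.1 requires ICU care, mechanical ventilation, pneumonia and "APACHE II score ≥ 10 and ≤ 35 within 24 hours once subject has consented". Another candidate cause can usually be named. Fever shows the overlap: it is a sign to watch for after infusion (Protocol 6.4) and also a qualifying sign of the index pneumonia (Protocol 4.1, criterion 6c).
- *Timing.* Protocol 1.2 gives a serum half-life of about 3 weeks, and Protocol 8.3 collects events for 28 days after dosing. With simple exponential decline, and if that half-life holds in these patients, the fraction remaining at Day 28 is 0.5^(28/21) = 0.5^1.33 ≈ 0.40. Timing will therefore seldom exclude the drug within the collection window.

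Both points lead to the second row. The documents do not say what share of events will fall there.

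**Step 3. Can a size be given?** Let q be the share of time-consistent events that also have another possible cause. The share of 8.3.1 reactions that meet the literal *Yes* is 1 − q. Assumed values of 0.25, 0.50, 0.75 and 0.90 give 75%, 50%, 25% and 10%. This only restates the assumption. The remaining share q fails the literal *No* as well, so 1 − q does not predict how many events will be flagged.

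**Step 4. Check whether the rest of 8.3.3 closes the gap.** The reasonable-possibility sentence comments on the definition but leaves the no-other-cause condition standing. The list of factors treats other drugs and underlying disease as matters to weigh, whereas the *Yes* definition has already made them disqualifying. Section 8.3.3 therefore conflicts with itself as well as with 8.3.1.

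**Step 5. Apply the 8.3.1 standard to the same table.** With *Yes* defined as not ruled out and *No* as its complement, the first two rows become *Yes* and the last two *No*. Unclassified cells fall from 2 to 0.

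**The case against.** The strongest reply is that the text does not push in one direction. A reader might infer that related SAEs will be under-flagged because *Yes* is so strict. But *No* is just as strict, and with a half-life of about 3 weeks it is seldom met. The same event is barred from both, so the direction depends on what investigators do when neither definition fits. Some will follow the reasonable-possibility sentence and choose *Yes*. It can also be said that a cause which is merely conceivable has not been identified, so that being ventilated or on antibiotics does not by itself bar *Yes* for a particular event. Both arguments stand: under-flagging is possible, but the documents do not establish it.

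A reader might also infer that all safety reporting hangs on this field. It does not:

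- SAEs from randomization to 28 days after dosing go to the CRO within 24 hours whatever their causality (Protocol 8.5).
- The DMC regularly reviews safety data with access to unblinded reports, and the Medical Monitor can convene it over an unusual frequency of unrelated events (Protocol 9.4).
- All-causality TEAEs, SAEs and AEs leading to death are tabulated (SAP 6.6.1), and the flag does not affect that comparison between arms.
- A missing relationship is counted as related in analysis (SAP 6.1.5).
- Protocol 8.7 places SUSAR reporting with the sponsor or CRO and does not tie it to the yes/no field. An unexpected reaction is defined in 8.3.2 as a kind of adverse reaction, the term that 8.3.1 defines broadly.

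These points limit the reach of the problem without removing it. The SAP rule for missing values acts only on a blank field, so it cannot correct an event marked *No* and does not reach DMC notification. Section 8.7 does not say whose causality judgement decides, so an effect on SUSAR identification remains possible.

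**Conclusion.** The defect is in the text and needs no assumption: two of four combinations have no category, and one of them is a reaction under 8.3.1. That it matters in practice rests on a judgement, well supported by the eligibility criteria and the half-life but not counted anywhere, that events with plausible timing and another possible cause will be common here. On that basis relatedness is likely to be flagged inconsistently and may be under-flagged.

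The direct effects are on immediate DMC communication of related SAEs, SAE reports after the 28-day period and the drug-related tables. An effect on SUSAR identification is possible. The problem is misclassification, with possible delay in escalation. Within 28 days it is not a failure to report SAEs, and no efficacy analysis is touched. No percentage of missed events can be supported from the documents. The inconsistency should be corrected, because the protocol already contains a workable standard.

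**What to change.** Reconcile Section 8.3.3 with 8.3.1:

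- Define *Yes* as at least a reasonable possibility that study drug caused the event, meaning that the relationship cannot be ruled out.
- Define *No* as everything else, so that the two categories cover all events.
- Keep other drugs, underlying disease and complications in the list of factors to weigh, and remove them as conditions of either category.
- Carry the same wording into the eCRF completion guideline, and state in 8.7 whose causality assessment determines a SUSAR.

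The cost is a wording change in the protocol and the eCRF guideline, with no new data collection. The downside is that more events will be classed as related and sent to the DMC, some of them due to the underlying illness. The placebo arm and the all-causality tables allow that extra volume to be read in context. If events have already been assessed under the present wording, the sponsor should decide before unblinding whether to have them reassessed.
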